11.3.2 Serious Adverse Event Reporting

In the event of any SAE reported or observed during the study (whether or not attributable to the study drug), investigational site personnel will report it immediately (within 24 hours of becoming aware of the SAE) by telephone call, fax, or email to Allakos, Inc.

Serious Adverse Event Report Forms will be provided to the investigational site to assist in collecting, organizing, and reporting SAEs, and follow-up information will be completed within 24 hours.

The Investigator will notify the Institutional Review Board (IRB)/Independent Ethics Committee (IEC) according to its guidelines. All SAE forms will be completed within 24 hours. All efforts will be made to obtain accurate and complete medical records for the SAE.

The patient’s condition will be followed by the Investigator or designated Sub-investigator. If additional visits are required, the patient will be asked to return to the clinic for further follow-up. As additional information becomes available, such as hospital discharge notes and patient medical records, the Investigator will be notified and provided with all relevant information.

All SAEs that have not resolved by the end of the study or that have not resolved upon discontinuation of the patient’s participation in the study must be followed until any of the following occurs:

- The event resolves

- The event stabilizes
- The event returns to Baseline, if a Baseline value is available
- The event can be attributed to agents other than the investigational product or to factors unrelated to study conduct
- It becomes unlikely that any additional information can be obtained (patient or health care practitioner refuses to provide additional information, patient is lost to follow-up after demonstration of due diligence with follow-up efforts)

11.3.3 Pregnancy

Female patients must inform the study Investigator immediately if they become pregnant during the study.

The Investigator must report any pregnancy to Allakos, Inc. within 24 hours of becoming aware of it using the provided pregnancy reporting forms. The patient must be immediately discontinued from further treatment with study drug. An uncomplicated pregnancy will not be considered an AE or SAE, but all pregnancies will be followed through term.

Pregnancies are reported if they occur in female patients or in the sexual partners of male patients from the time the patient is first exposed to the investigational product until Day 168 or ET.

Any congenital abnormalities noted at birth in the offspring of a patient who received study drug will be reported as an SAE. The outcome of any pregnancy and the presence or absence of any congenital abnormality will be recorded in the source documentation and reported to the Medical Monitor and Sponsor.

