6.2 Inclusion Criteria

Patients are eligible for the study if all of the following criteria are met:

1. Written informed consent
2. Male and female patients aged ≥ 18 and ≤ 75 years at the time of Screening
3. SNOT-22 (Appendix 5 [Section 19.5](#)) ≥ 30
4. At Screening, TPS of ≥ 5 for both nostrils with presence on endoscopy of nasal polyps of grade ≥ 2 in each nostril according to the polyp grading scale (Appendix 2 [Section 19.2](#))
Polyp grading scale for each nostril:
0=no nasal polyps
1=small polyps in the middle meatus not reaching below the inferior border of the middle turbinate
2=polyps reaching below the lower border of the middle turbinate
3=large polyps reaching the lower border of the inferior turbinate or polyps medial to the middle turbinate
4=large polyps causing complete obstruction of the inferior nasal cavity
5. History of at least 2 of the following symptoms for 4 weeks prior to Screening:
 - a) Anterior nasal discharge
 - b) Posterior nasal discharge
 - c) Nasal congestion, blockade, or obstruction

- d) Decreased sense of smell
- e) Facial pain or pressure
- 6. Received continuous topical nasal steroids and/or leukotriene receptor antagonists for at least 8 weeks prior to Screening unless failure or no effect of prior nasal steroid or leukotriene receptor antagonist therapy is documented
- 7. At randomization, received $\geq 80\%$ of doses of NASONEX scheduled during the Run-in period
- 8. At randomization, TPS of ≥ 5 for both nostrils with presence on endoscopy of nasal polyps of grade ≥ 2 in each nostril according to the polyp grading scale (see Inclusion Criterion #4 and Appendix 2 [Section 19.2](#)) and despite prior INS treatment during the Run-in period
- 9. Female patients must be post-menopausal for ≥ 1 year with documented follicle-stimulating hormone (FSH) > 30 IU/L, surgically sterile (tubal ligation, hysterectomy, or bilateral oophorectomy) for at least 3 months, or, if of child-bearing potential, willing to use a highly effective method of contraception (Appendix 1 [Section 19.1](#)) from Screening until at least 17 weeks after the last dose of the study drug is administered, which corresponds to approximately 5 half-lives of AK001

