- 10. Male patients with female partners of childbearing potential must agree to use a highly effective method of contraception (Appendix 1 [Section 19.1](#)) from Screening until at least 17 weeks after the last dose of the study drug is administered, which corresponds to approximately 5 half-lives of AK001. All fertile men with female partners of childbearing potential should be instructed to contact the Investigator immediately if they suspect their partner might be pregnant (e.g., missed or late menstrual period) at any time during study participation.
- 11. Negative Screening ova and parasite test
- 12. No clinically significant Screening 12-lead ECG, vital sign, hematology, chemistry, or urinalysis findings
- 13. Able to comply with all study procedures including recording scores of symptoms (i.e., anterior nasal discharge; posterior nasal discharge, nasal congestion, blockade, or obstruction; decreased sense of smell; facial pain or pressure) at clinic visits

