12 DISCONTINUATION AND REPLACEMENT OF PATIENTS

12.1 Early Discontinuation of Study Drug

A patient may be discontinued from study treatment at any time if the patient, the Investigator, or the Sponsor feels that it is not in the patient's best interest to continue. The following is a list of possible reasons for study treatment discontinuation:

- Patient's withdrawal of consent
- Patient is not compliant with study procedures
- AE that, in the opinion of the Investigator, results in it being in the best interest of the patient to discontinue study treatment
- Protocol violation requiring discontinuation of study treatment
- Loss to follow-up
- Sponsor's request for ET of study
- Positive pregnancy test (females)

If a patient is withdrawn from treatment due to an AE, the patient will be followed and treated by the Investigator until the abnormal parameter or symptom has resolved or stabilized.

All patients who discontinue study treatment should come in for an ET visit as soon as possible.

All patients are free to withdraw from participation at any time for any reason, specified or unspecified, and without prejudice.

Reasonable attempts will be made by the Investigator to provide a reason for patient withdrawals. The reason for the patient's withdrawal from the study will be specified in the patient's source documents. Refer to [Table 1](#) for ET procedures.

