19 APPENDICES

19.1 Appendix 1: Contraception Guidelines

Contraception guidelines vary by location; local guidelines will be followed.

Female patients must be post-menopausal for at least 1 year with documented follicle-stimulating hormone (FSH) >30 IU/L, surgically sterile (tubal ligation, hysterectomy, or bilateral oophorectomy) for at least 3 months, or, if of child-bearing potential, willing to use a highly effective method of contraception from Screening until at least 17 weeks after the last dose of the study drug is administered, which corresponds to approximately 5 half-lives of AK001.

Male patients with female partners of childbearing potential must agree to use a highly effective method of contraception from Screening until at least 17 weeks after the last dose of the study drug was administered, which corresponds to approximately 5 half-lives of AK001. All fertile men with female partners of childbearing potential should be instructed to contact the Investigator immediately if they suspect their partner might be pregnant (e.g., missed or late menstrual period) at any time during study participation.

Highly effective methods of contraception include the following practices:

- a) Complete abstinence (acceptable only if it is established before the patient participates in the trial that this is the preferred and usual lifestyle of the patient)
- b) Prescription hormonal contraceptives (oral, injected, or implanted) for 2 or more menstrual cycles prior to Screening
- c) Intrauterine device
- d) Surgical sterilization for male patients with female partners
 - i. Tubal ligation/hysterectomy/bilateral oophorectomy or
 - ii. Vasectomy

The double barrier method of contraception (e.g., condom with cap, diaphragm, or sponge with spermicide) alone is not considered a highly effective method but may be used in conjunction with 1 of the above methods.

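### For patients who leave early, pregnancy reporting can stop well before the 17-week post-dose contraception period ends

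*Protocol*

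**What the plan says.** Protocol section 11.3.3 limits pregnancy reporting, for female patients and for the partners of male patients, to the period "from the time the patient is first exposed to the investigational product until Day 168 or ET".

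The contraception requirement follows a different clock. Inclusion Criteria 9 and 10 (section 6.2) require it "from Screening until at least 17 weeks after the last dose of the study drug is administered". Appendix 1 (section 19.1) repeats this and gives the reason: "17 weeks after the last dose of the study drug was administered, which corresponds to approximately 5 half-lives of AK001".

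The patient's duty to tell the site is worded separately for each sex:
- Women (11.3.3): "Female patients must inform the study Investigator immediately if they become pregnant during the study".
- Men (Inclusion Criterion 10, repeated in Appendix 1) are to contact the Investigator "if they suspect their partner might be pregnant (e.g., missed or late menstrual period) at any time during study participation".

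On the timing of the early termination (ET) visit, section 12.1 says: "All patients who discontinue study treatment should come in for an ET visit as soon as possible". Section 12.2 treats stopping treatment early as withdrawing before Day 168.

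Two sentences in 11.3.3 carry no end date: "The Investigator must report any pregnancy to Allakos, Inc. within 24 hours of becoming aware of it", and "Any congenital abnormalities noted at birth in the offspring of a patient who received study drug will be reported as an SAE".

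**The concern.** The contraception clock starts at the last dose and takes no account of ET. The reporting clock stops at ET. A patient who stops treatment and attends the ET visit promptly therefore leaves the reporting window while still under the contraception requirement, at a time when the protocol itself regards drug persistence as relevant to pregnancy.

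The duty to inform appears to lapse at about the same time. The men's wording is tied to participation. The women's is tied to the study, which for an individual patient most naturally means her own time in it. The protocol schedules no contact after ET for the remainder of the 17 weeks.

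What is at stake is information only. A pregnancy that begins after ET but within 17 weeks of an AK001 dose may never reach the sponsor. Because the sentences of 11.3.3 pull in different directions, sites could also handle the same case differently. The contraception requirement itself is not shortened.

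**Working it through.** **Inputs**
- Dosing on Days 0, 21 and 49 (sections 4.1 and 8.5.2).
- Contraception for at least 17 weeks after the last dose (section 6.2, Appendix 1).
- Reporting until Day 168 or ET (section 11.3.3).
- Visit windows Day 49 ±2 and Day 168 ±7 (Table 1).
- Half-life 20 to 27 days (section 2).
- Dropout rate and timing: not given. ET is assumed to fall on scheduled visit days.

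**The protocol's own figures**
- 17 × 7 = 119 days, and Day 49 + 119 = Day 168. For a completer at nominal days both periods end together.
- 119/27 = 4.4 and 119/20 = 5.95 half-lives, which agrees with the stated figure of about five.

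**Shortfall for early terminators**

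End of contraception = last dose day + 119. Shortfall = 119 − d, where d is the number of days from last dose to ET.

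| Doses received | Last dose | Contraception to | Assumed ET | d | Shortfall | Share of 119 days |
|---|---|---|---|---|---|---|
| 1 | Day 0 | Day 119 | Day 21 | 21 | 98 days | 82% |
| 2 | Day 21 | Day 140 | Day 49 | 28 | 91 days | 76% |
| 3 | Day 49 | Day 168 | Day 84 | 35 | 84 days | 71% |
| 3 | Day 49 | Day 168 | Day 112 | 63 | 56 days | 47% |

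The largest possible value is about 118 days (ET the day after a dose). The shortfall is zero only if ET falls 17 weeks or more after the last dose.

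**Completers**

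The visit windows alone leave at most 51 + 119 − 161 = 9 days, and only if the last dose is as late and the final visit as early as allowed. The point does not depend on this.

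**Drug remaining (context only)**

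Assuming simple exponential decline, the fraction left 28 days after the last dose is 2^(−28/20) = 0.38 to 2^(−28/27) = 0.49.

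**Other text that might close the gap**
- The duty to report any pregnancy starts when the Investigator becomes aware of it. Awareness depends on the patient speaking up, and a later paragraph of 11.3.3 limits which pregnancies are reported.
- The congenital-abnormality sentence likewise helps only if the site learns of the birth.
- The ET pregnancy test (9.3.4) covers female patients, and only pregnancies already detectable at that visit.
- The final visit for those who withdraw after Day 84 (12.2) is only encouraged, has no set timing and omits earlier withdrawals.

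**The case against.** The strongest reply is that nothing is contradicted. A contraception period and a reporting window serve different purposes, no text says they must coincide, and Day 168 or ET is also the end point for AEs and SAEs (9.2.8, 11.3.1). Section 11.3.3 also has undated duties: to report any pregnancy, to follow all pregnancies to term, and to treat congenital abnormalities as SAEs. This much stands: 11.3.3 is ambiguous and does not flatly exclude a late pregnancy. The undated duties soften the gap without closing it, because the same section then states an end date.

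A second reply is that the women's duty to inform may outlast one patient's ET, since 11.3.2 distinguishes the end of the study from the end of a patient's participation. That reading is possible but not the natural one for an instruction to an individual. The men's wording is plainly tied to participation.

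Third, exit instructions could sit in the consent form or the pregnancy reporting forms, which are not available here. That is fair, and the point is therefore confined to the protocol text. It would still leave the stated end date in 11.3.3 to be corrected.

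Finally, the numbers affected are small. Of the 70 patients, 20 receive placebo, and the background section puts peak incidence at 40 to 60 years with a 2:1 male preponderance, so few women of childbearing potential are likely. This stands and supports a low rating. The male preponderance does not reduce the relevance of partner pregnancies, where the wording gap is clearest.

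**Conclusion.** The concern holds as a minor point of safety reporting. For early terminators the stated pregnancy-reporting window, and on its natural reading the duty to inform, can end before the 17-week contraception period does. On ET dates assumed at scheduled visits, the shortfall is 98, 91 or 84 days after one, two or three doses with ET at Days 21, 49 and 84. It is zero for completers at nominal days.

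The pregnancies concerned are those that begin after ET and within 17 weeks of the last dose, in a patient or partner of childbearing potential. Few are expected, though the number cannot be estimated without a dropout rate. No endpoint, analysis or power calculation is affected.

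**What to change.** - In section 11.3.3, have pregnancies reported from first exposure until the later of Day 168/ET and 17 weeks after the last dose. The window would then run to at least Day 119, 140 or 168 after one, two or three doses at nominal days, and the shortfall would be zero.
- Extend the duty to inform to the same date, for women in 11.3.3 and for men in Inclusion Criterion 10 and Appendix 1.
- At the ET visit, instruct patients to notify the site of any pregnancy up to that date. This is the main measure.
- Optionally, add one telephone contact at about 17 weeks after the last dose for early terminators who still consent. A very recent conception may not yet be recognised at that call, so it cannot replace the ET instruction.

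The AE and SAE windows need no change.

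The cost is a few sentences in the next amendment, with IRB/IEC approval, and a little site time. Patients who withdraw consent or are lost to follow-up will remain out of reach.

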11.4 Anaphylaxis

Signs or symptoms of anaphylaxis will be carefully monitored and treated according to standard of care. Emergency crash cart equipment will be available at all times during the conduct of the study.

12 DISCONTINUATION AND REPLACEMENT OF PATIENTS

12.1 Early Discontinuation of Study Drug

A patient may be discontinued from study treatment at any time if the patient, the Investigator, or the Sponsor feels that it is not in the patient's best interest to continue. The following is a list of possible reasons for study treatment discontinuation:

- Patient's withdrawal of consent
- Patient is not compliant with study procedures
- AE that, in the opinion of the Investigator, results in it being in the best interest of the patient to discontinue study treatment
- Protocol violation requiring discontinuation of study treatment
- Loss to follow-up
- Sponsor's request for ET of study
- Positive pregnancy test (females)

If a patient is withdrawn from treatment due to an AE, the patient will be followed and treated by the Investigator until the abnormal parameter or symptom has resolved or stabilized.

All patients who discontinue study treatment should come in for an ET visit as soon as possible.

All patients are free to withdraw from participation at any time for any reason, specified or unspecified, and without prejudice.

Reasonable attempts will be made by the Investigator to provide a reason for patient withdrawals. The reason for the patient's withdrawal from the study will be specified in the patient's source documents. Refer to [Table 1](#) for ET procedures.

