4.2 Schedule of Events

Table 1 Schedule of Events

Procedure	Screening Period	Run-in Period ¹		Treatment Period									Post-treatment Period			
	Screening	Run-in ²	Day -3	Day 0		Day 1	Day 14	Day 21		Day 22	Day 49		Day 50	Day 84	Day 112	Day 168/ET
Days	-56 to -29 ³	-28 ⁴	-3±2	0 (Pre-dose)	0	1	14±2	21±2 (Pre-dose)	21±2	22±2	49±2 (Pre-dose)	49±2	50±2	84±4	112±4	168±7 (or ET)
Weeks	-8 to -5	-4 ⁵	-1	0	0	0	2	3	3	3	7	7	7	12	16	24
Informed consent	X															
Eligibility assessment	X		X													
Randomization				X ⁶												
Intranasal steroid adjustment ⁷		X														
Study drug ⁸				X				X			X					
Medical history ⁹	X															
Complete PE ¹⁰	X															
Symptom-directed PE ¹¹				X	X		X	X	X		X	X		X	X	X
Follow-up telephone call ¹²					X	X			X	X		X	X			

Procedure	Screening Period	Run-in Period ¹		Treatment Period									Post-treatment Period			
	Screening	Run-in ²	Day -3	Day 0		Day 1	Day 14	Day 21		Day 22	Day 49		Day 50	Day 84	Day 112	Day 168/ET
Days	-56 to -29 ³	-28 ⁴	-3±2	0 (Pre-dose)	0	1	14±2	21±2 (Pre-dose)	21±2	22±2	49±2 (Pre-dose)	49±2	50±2	84±4	112±4	168±7 (or ET)
Weeks	-8 to -5	-4 ⁵	-1	0	0	0	2	3	3	3	7	7	7	12	16	24
Body weight and height ¹³	X			X											X	X
Vital signs ¹⁴	X		X	X ¹⁵	X ¹⁵		X	X ¹⁵	X ¹⁵		X ¹⁵	X ¹⁵		X	X	X
12-lead ECG	X															
Serum pregnancy test and FSH (if indicated) ¹⁶	X		X					X			X					X
Fecal sample for ova and parasites	X															
HIV, HBV surface antigen, HCV antibody	X															
Hematology ¹⁷	X		X				X	X			X			X	X	X
Chemistry ¹⁷	X		X				X	X			X			X	X	X
Urinalysis	X		X				X				X			X	X	X
Nasal endoscopy ¹⁸	X		X					X			X			X	X	
CT scan			X ¹⁹											X ¹⁹		

Procedure	Screening Period	Run-in Period ¹		Treatment Period									Post-treatment Period			
	Screening	Run-in ²	Day -3	Day 0		Day 1	Day 14	Day 21		Day 22	Day 49		Day 50	Day 84	Day 112	Day 168/ET
Days	-56 to -29 ³	-28 ⁴	-3±2	0 (Pre-dose)	0	1	14±2	21±2 (Pre-dose)	21±2	22±2	49±2 (Pre-dose)	49±2	50±2	84±4	112±4	168±7 (or ET)
Weeks	-8 to -5	-4 ⁵	-1	0	0	0	2	3	3	3	7	7	7	12	16	24
PNIF				X				X						X	X	
UPSIT				X			X	X			X			X	X	
SNOT-22	X			X			X	X			X			X	X ²⁰	
VASs and clinical symptoms improvement scale ²¹	X	X	X	X			X	X			X			X	X ²⁰	
SF-36				X				X			X			X	X	
Spirometry ²²	X							X			X					
ACT ²³	X			X				X			X			X	X ²⁰	
Blood for PK				X ²⁴			X	X ²⁴			X ²⁴			X	X	X
ADA ²⁵				X											X	X
Blood for potential exploratory biomarker analysis ²⁶			X					X			X			X		
Total serum IgE			X													
ImmunoCAP test			X													

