15. On Days 0, 21 and 49, vital signs will be measured pre-dose, every 15 minutes after the start of infusion, and immediately following the end of infusion.
16. For all female patients, blood will be obtained for a serum pregnancy test at Screening, and blood or urine is to be obtained for pregnancy tests on Day -3, pre-dose on Days 21 and 49, and on Day 168 or ET. Blood for FSH is to be obtained only at Screening to confirm postmenopausal status (FSH level >30 IU/L).
17. Patients will refrain from alcohol and strenuous exercise (e.g., heavy lifting, weight training, aerobics) for at least 48 hours and fast overnight (8 hours) from food and beverages other than water prior to each blood collection for clinical safety laboratory tests as detailed in [Section 9.3.3](#).
18. Nasal endoscopies (blinded centralized evaluation) will be performed at Screening, on Day -3, pre-dose on Days 21 and 49, and on Days 84, and 112 or ET for efficacy analyses.
19. CT scans will be performed at selected Investigator sites on Day -3 and on Day 84 or ET. CT scans are optional and will only be done at Investigator sites at which appropriate and timely regulatory approval or authorization can be granted.
20. These evaluations will be performed only at ET if not obtained on Day 112.
21. Patients will complete VASs and the clinical symptoms improvement scale at Screening; at start of Run-in; on Day -3; pre-dose on Days 0, 21, and 49; and on Days 14, 84, and 112 or ET. The VASs and clinical symptoms improvement scale will be completed at clinic visits; however, if the Run-in clinic visit is replaced by telephone contact, the patient will complete the scales at home and bring them to the next (Day -3) clinic visit.
22. Spirometry will be performed at Screening and pre-dose on Days 21 and 49 to assess FEV1, FVC, and FEF.
23. The ACT will be performed only in patients with comorbid asthma.
24. Blood samples for PK on Days 0, 21, and 49 will be obtained pre-dose.
25. Blood samples for ADA will be collected pre-dose on Day 0 and, should a related AE suspected of being associated with immunogenicity occur, post-dose, as well as on Day 112 and Day 168 or ET.
26. Blood samples (5 mL serum, 5 mL plasma, and 5 mL RNAlater solution) will be obtained on Day -3, pre-dose on Days 21 and 49, and on Day 84 and stored.
27. All prior medications, including both prescribed and over-the-counter medications, started within the 30 days before Screening will be recorded.

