12.2 Withdrawal of Patients from the Study

Participation of a patient will be discontinued in the event that:

- An AE or SAE that, in the judgment of the Investigator, requires treatment withdrawal due to its nature, severity, or required treatment, regardless of the causal relationship to treatment
- Protocol violations, including non-compliance, loss to follow-up

- Occurrence of an exclusion criterion that is clinically relevant and affects the patient's safety, if discontinuation is considered necessary by the Investigator and/or Sponsor
- Serum transaminases (ALT and/or AST) $>3 \times$ upper limit of normal (ULN) AND total bilirubin $>2 \times$ ULN (confirmed by subsequent repeat) without an alternative explanation
- Elevation of ALT or AST $>3 \times$ ULN (confirmed by repeat) with the appearance or worsening of symptoms felt by the Investigator to be potentially related to hepatic inflammation, such as fatigue, nausea, vomiting, right upper quadrant pain or tenderness, fever, rash, or eosinophilia
- Use of a non-permitted concomitant drug, as defined in [Section 7.1](#)
- Withdrawal of the patient's consent
- Participation in any other trial during the duration of this trial
- Loss of ability to freely provide consent through imprisonment or involuntary incarceration for treatment of either a psychiatric or physical (e.g., infectious disease) illness
- Discretion of the Investigator

All patients are free to withdraw from participation at any time for any reason specified or unspecified, and without prejudice.

Reasonable attempts will be made by the Investigator to provide a reason for patient withdrawals. The reason for the patient's withdrawal from the study will be specified in the patient's source documents. As noted above, patients who discontinue study treatment early (i.e., they withdraw prior to Day 168) should have an ET visit. Refer to [Table 1](#) for ET procedures. Patients who withdraw after Day 84 but prior to Day 168 should be encouraged to come in for a final visit.

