15.1.3 Efficacy Populations

The main population for efficacy will be the Modified Intention-to-Treat Population, defined as all patients randomized who receive at least 1 dose of study drug and have a valid Baseline measurement and at least 1 post-baseline efficacy assessment. Patients will be analyzed for efficacy according to the group to which they were randomized.

In addition, the primary efficacy analyses will also be performed for the Per-Protocol Population, defined as patients who have a Week 12 visit and valid efficacy measurements.

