15.3 Analysis of Primary Endpoint

The effect of 2 different dose levels of AK001 in combination with an INS versus the INS alone on the reduction in size of nasal polyps as evaluated by the change from Baseline to

Week 12 after the start of treatment in TPS (Appendix 2 [Section 19.2](#)) will be displayed for each treatment group by study visit using summary statistics, including the number of observations, the mean, median, standard deviation (SD), and range. Each active treatment group will be compared separately with the placebo group for change from Baseline in TPS by using a mixed effect repeated measures analysis of variance (ANOVA) model with specific contrast statement for Week 12 and for each comparison separately. Adjustment in alpha for multiple comparisons will be controlled according to the Hochberg method, in which, if the efficacy comparison of the high active arm versus placebo is statistically significant at the 0.05 level, no penalty will be assessed to the comparison of the low active arm versus the placebo arm. Otherwise, the low active arm versus the placebo arm will be compared at the 0.025 level.

Missing values for the primary endpoint will be imputed by 2 methods: last observation carried forward and worst observation carried forward. Imputations will be done on the total score level and not on the individual item level. Due to the sample size, no multiple imputation technique is intended.

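### Sections 12.1 and 12.2 treat stopping study drug as leaving the study, so patients who stop early lose their Week 12 polyp score by rule

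*Protocol*

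**What the plan says.** Study drug is given on Days 0, 21 and 49. Section 9.6.3 makes the primary endpoint the reduction in TPS from Baseline to Week 12, which Table 1 places at Day 84±4.

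- **Section 12.1**, on stopping study drug: "All patients who discontinue study treatment should come in for an ET visit as soon as possible". Patients withdrawn from treatment for an adverse event are followed until it resolves or stabilises, but no endoscopy is attached to that follow-up.
- **Section 12.2**, on leaving the study: "patients who discontinue study treatment early (i.e., they withdraw prior to Day 168) should have an ET visit". Its list of reasons that end participation includes "An AE or SAE that, in the judgment of the Investigator, requires treatment withdrawal due to its nature, severity, or required treatment". The only later visit it encourages is this: "Patients who withdraw after Day 84 but prior to Day 168 should be encouraged to come in for a final visit".
- **Section 15.1.3** defines mITT as randomized patients who received at least one dose and "have a valid Baseline measurement and at least 1 post-baseline efficacy assessment". A Week 12 TPS is not required.
- **Section 15.3**: "Missing values for the primary endpoint will be imputed by 2 methods: last observation carried forward and worst observation carried forward".
- **Section 12.3**: patients who withdraw are not replaced.
- **ET endoscopy**: Sections 12.1 and 12.2 refer to Table 1 for early termination (ET) procedures. The row "Nasal endoscopy ¹⁸" is blank under the combined Day 168/ET column, while footnote 18 places endoscopy "pre-dose on Days 21 and 49, and on Days 84, and 112 or ET for efficacy analyses". Sections 9.6.3 and 9.6.4 agree with the footnote.

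**The concern.** Stopping an infusion and leaving a trial are different events, and the protocol merges them. Section 12.2 shows this most plainly. The last dose is on Day 49, yet early discontinuation of treatment is defined by withdrawal up to Day 168. After Day 49 there is no treatment left to stop, so the definition can only mean leaving the study.

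A patient who stops drug but would still attend is therefore closed out at once, and the Day 84 endoscopy is not done. mITT keeps that patient, so the Week 12 value must be imputed or modelled. What happened to polyp size after stopping then becomes an assumption that nobody can check. The order and role of imputation methods can be settled later in a SAP. A missed endoscopy cannot.

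**Working it through.** **1. Who is affected.** From the Day 49 dose to the Day 84 endoscopy is 84 − 49 = 35 days. Anyone who stops before the Day 49 dose and has the ET visit promptly leaves nominally 35 days or more too early. An ET visit that happened to fall within Day 84±4 would be an exception. Patients who leave after Day 84, the only group encouraged to return, already have the Week 12 score.

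**2. The plan's own figure.** Inputs from Section 15.7: mean change −1.9 (SD 2.064, n=25) against −0.3 (SD 1.128, n=20), alpha 0.05, taken as two-sided.

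- Difference: −1.9 − (−0.3) = −1.6.
- SE = √(2.064²/25 + 1.128²/20) = √(0.1704 + 0.0636) = 0.484.
- Ratio: 1.6/0.484 = 3.31. Power is 91.1% by normal approximation and 89.7% by Welch t.

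The stated power of at least 80% is reproduced, with a Week 12 score in every patient.

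**3. Size of the gap.** The protocol gives neither a stopping rate nor an off-drug course for TPS, so both are assumed. Let s be the share who stop before the Day 49 dose and L the share of the effect they have lost by Day 84. The target is the effect in all patients, including values after stopping.

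- True effect = −1.60 × (1 − s × L).
- A repeated measures model without the stoppers' Day 84 scores estimates −1.60, because it treats them as if they had kept the effect.
- Overstatement = 1.60 × s × L.

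| s | Half lost: true effect, gap | All lost: true effect, gap |
|---|---|---|
| 5% | −1.56, 0.04 | −1.52, 0.08 |
| 7.5% | −1.54, 0.06 | −1.48, 0.12 |
| 10% | −1.52, 0.08 | −1.44, 0.16 |

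Against the SE of 0.484, the gap runs from 0.04/0.484 = 0.08 to 0.16/0.484 = 0.33 of a standard error.

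**4. Carrying a score forward.** Further assumptions: the effect builds from −0.5 at Day 21 to −1.0 at Day 49 and −1.6 at Day 84, and 15% of patients lack a Day 84 score. Half of these stopped between Days 21 and 49, and half left after Day 49. Last observation carried forward then gives:

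- without an ET score: 0.85(−1.6) + 0.075(−0.5) + 0.075(−1.0) = −1.47;
- with an ET score midway between visits: 0.85(−1.6) + 0.075(−0.75) + 0.075(−1.3) = −1.51.

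The result is the same whatever the stoppers' true Day 84 scores are.

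**5. Effect of keeping the visit.** This was simulated with 20,000 trials per scenario, 15% missing, 7.5% stoppers and within-patient correlation 0.7 (assumed). The model estimates, with none, half or all of the stoppers seen at Day 84, were:

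- half the effect lost (true −1.54): −1.60, −1.57, −1.53;
- all of it lost (true −1.48): −1.60 (−1.605 unrounded), −1.53, −1.47.

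Missing Week 12 scores fall from 15% to about 11% and then to 7.5%. The estimate moves to the true value as scores are collected.

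**The case against.** **The group is small.** There are only three infusions. Section 12.1's reasons for stopping include withdrawal of consent, loss to follow-up and termination by the sponsor, which no visit rule can reach. This stands and limits the gain.

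**Total loss of effect is unlikely, at least at the higher dose.** Section 2 reports a half-life of 20 to 27 days and receptor internalization lasting as long as drug is in serum. From a Day 21 dose to Day 84 is 63 days, or 63/27 = 2.3 to 63/20 = 3.2 half-lives, leaving roughly 20% to 11% of that dose by terminal half-life alone. For 250 mg that is about 50 to 28 mg, still above the 25 mg dose that Section 15.7 assumes to be equally effective. The all-lost column is therefore an extreme.

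**A reader might infer that last and worst observation carried forward must be ranked, and that the model on observed scores should be primary.** The documents do not support this as a finding. Section 15 leaves full detail on data handling to the SAP. The figures do not favour that model when no off-drug scores are kept: with 7.5% stoppers who lose everything, it gives −1.60 and carrying forward gives −1.47 to −1.51, against a true −1.48.

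**A reader might infer that it is undetermined whether ET includes endoscopy, so that someone who leaves between Days 14 and 21 has no post-baseline TPS.** That reading sets aside footnote 18, which is part of Table 1, and two sections that agree with it. A mark in the combined column would also order a Day 168 endoscopy, which may explain the blank. The rows for PNIF, UPSIT and SF-36 are blank there too, although their sections also provide for ET. This is a minor table inconsistency.

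**A reader might infer that the power statement is wrong.** It reproduces from its own inputs. Welch power falls to 77.4% if 20% of both arms stop and Baseline is carried forward (difference 0.8 × 1.6 = 1.28), but that rate and that handling are assumptions.

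**Conclusion.** The point holds in one specific form. Sections 12.1 and 12.2 do not separate stopping drug from leaving the study. Patients who stop before the Day 49 dose therefore lose the primary score by rule while remaining in mITT, and no later document can restore it.

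The numerical effect is modest and uncertain. The bias avoided is about 0.04-0.08 TPS points if half the effect is lost and at most about 0.16 if all is lost, or no more than a third of a standard error. This rests on an assumed 5-10% stopping before Day 49, the planning difference of −1.6, and a target effect that includes values after stopping. The case for change is that the loss is avoidable and irreversible, not that it is large. The blank ET cell in Table 1 is a clerical matter.

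**What to change.** 1. In Sections 12.1 and 12.2, distinguish stopping study drug from leaving the study. Ask patients who stop drug but do not withdraw consent to keep the scheduled visits, at least the Day 84 endoscopy. Reserve the ET visit for those who leave.
2. Reconcile this with the Section 12.2 list of reasons that end participation. No criterion for stopping drug needs to change.
3. Use the retained Day 84 scores in the Week 12 mITT analysis.
4. As a minor edit, align the endoscopy row of Table 1 with footnote 18 and Sections 9.6.3 and 9.6.4.

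The cost is text in two sections, a line on the use of retained scores and one table row. At an assumed 5-10% stopping, 0.05 × 70 = 3.5 to 0.10 × 70 = 7, so about 4 to 7 patients would keep visits that already exist. Only consenting drug-stoppers are reached, and some will decline. Off-drug scores may lower the estimate and power: in the extreme case of 7.5% stoppers, all retained and with the effect wholly lost, the simulation gives −1.47 and about 81% power, against 86% for the model when those scores are missing and the effect is kept. Scores taken after a drug not permitted by Section 7.1 will be harder to interpret. Their handling can be set in the SAP.
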